At each contact with the subject, the investigator will seek information on adverse events by continuous monitoring while subject is under anesthesia, specific questioning and, as appropriate, by examination. Information on all adverse events will be recorded immediately in the source document, and also in the appropriate adverse event module of the case report form (CRF). All clearly related signs, symptoms, and abnormal diagnostic procedures results will be recorded in

the source document, though should be grouped under one diagnosis. All adverse events occurring during the study period will be recorded. The clinical course of each event will be followed until resolution, stabilization, or until it has been determined that the study treatment or participation is not the cause. Serious adverse events that are still ongoing at the end of the study period will be followed up to determine the final outcome. Any serious adverse event that occurs after the study period and is considered to be possibly related to the study treatment or study participation will be recorded and reported immediately.

l. Reporting of Serious Adverse Events

Reports of all serious adverse events (including follow-up information) will be submitted to the IRB according to their policies. Copies of each report and documentation of IRB notification and receipt will be kept in the research binder.

m. Unblinding Procedure

The unblinding procedure will ensure that the identity of the investigational medicinal product is only revealed as far as necessary. The subject's treatment will be revealed when it is necessary to ensure the subject's safety and/or this information would be instrumental in further treatment decisions during a medical emergency and/or a suspected unexpected serious adverse event. Pharmacy personnel with access to the randomization scheme will be contacted using a designated telephone number. If a subject's treatment is unblinded, this will be reported to the IRB as per guidelines and documented on the CRF (date and initials of investigator) with details of the time and reason for unblinding.

n. Stopping Rules

This study will be stopped prior to its completion if: (1) the intervention is associated with adverse effects that call into question the safety of the intervention; (2) any new information becomes available during the trial that necessitates stopping the trial; or (3) other situations occur that might warrant stopping the trial.

o. Medical Monitoring/ Data and Safety Monitoring Plan

In accordance with federal guidelines, this study requires a DSMP. It is the responsibility of the Principal Investigator to oversee the safety of the study at his/her site. This safety monitoring will include careful assessment and appropriate reporting of adverse events as noted above, as well as the construction and implementation of a site data and safety-monitoring plan. Medical monitoring will include a regular assessment of the number and type of serious adverse events.

The PI has appointed an independent Safety Officer/Medical Monitor to fulfill the data and safety monitoring responsibilities. The director of Regional Anesthesia at Northwell Health and medical director of Franklin Hospital, [name] MD, will serve as the data and safety monitor along with [name], who will offer ancillary support to the monitoring responsibilities. [name] does not have any scientific, financial, or other conflict of interest related to the study and is not responsible for any patient care at Long Island Jewish Medical Center. Safety will be

monitored after the first 5 patients and at 6 month intervals afterwards by the study team and the Safety Officer/Medical Monitor throughout the duration of the study. The PI will prepare a safety report for these regular reviews comprised of adverse events and the actions taken. The PI will contact the Medical Monitor for ad hoc reviews of any unanticipated safety events. The study protocol will be carried out in accordance with OHRP/FDA/NIH guidelines and requirements. In the event of a serious adverse event during the study protocol, it will be reported immediately to the PI, the co-investigators, and the Medical Monitor. Serious AND Unanticipated AND possibly, probably or definitely related AEs will be reported to the IRB by the principal investigator as well as to all members of the research team. Data will also be reviewed to determine if aspects of the study need to be changed or stopped. In addition, the monitor will review any and all deviations, adverse events and unanticipated problems that may occur to determine their relatedness to the study, their severity, and whether they require study changes. In addition, any unanticipated problems will be reported to the IRB as per their specific reporting requirements. Anticipated deviations will be submitted to the IRB for approval as a protocol exception prior to its initiation, unless required to eliminate apparent immediate hazards.

The primary concern when administering local anesthetics is the development of local anesthetic toxicity or anaphylaxis. With respect to this study, the risks of local anesthetic toxicity after a serratus plane block is lower than most alternative regional techniques because a smaller dose of anesthetic is injected under ultrasound into a less vascularized area (Tighe 2013, Blanco et al 2013). With respect to anaphylaxis, patients with a suspected allergy to local anesthetics based on medical history and patient self report will be excluded from the study. Subjects will also be continuously monitored in the OR during the bupivacaine injection and for the duration of surgery for these potential adverse events by: electrocardiogram, blood pressure and arterial oxygen saturation. The PI (or another designated Investigator in his absence) will be notified of any abnormal results so that standard of care safety measures outlined are implemented. The primary physician will also be notified of any abnormal results and any changes to the subject's care, and will also be provided with the test results. The use of single-shot regional anaesthetic techniques is associated with few complications. The expected risks are as follows:

Allergic reaction, toxicity and effects associated with injection:

Monitoring: following first 5 subjects enrolled and at 6 month intervals.

Actions: If there is any indication of allergy to local anesthetics in patient medical records or patient reports allergy at screening, subject will not be enrolled. If there is any indication of allergic reaction during injection, injection will be discontinued immediately but patient will continue to be followed until end of study. Signs of allergy at any study visit, such as headache, dizziness, nausea, vomiting, hives and itching will be recorded as AEs. With respect to toxicity investigators will use slow, incremental injections of local anesthetic, while monitoring the patient for signs of toxicity. Early recognition of the toxicity and early discontinuation of the administration is of crucial importance. Any signs of toxicity such as hypotension, severe hypotension, reduced cardiac output, and/or malignant arrhythmias will result in the administration of local anesthetics being

stopped immediately and patient parameters will be continuously assessed until the patient is completely asymptomatic and stable and the event recorded as an AE. Events associated with injection include block failure, pain, infection, bruising/hematoma, nerve injury, and pneumothorax. Symptoms of injection related events will be treated and checked at appropriate intervals in addition to any other clinical testing requested by primary physician.

The clinical course of each event will be followed until resolution, stabilization, or until it has been determined that the study treatment or participation is not the cause.

p. Discontinuation of Study / Subject Withdrawal

Patients may withdraw from this study at their discretion. The study may be discontinued at any time at the discretion of the PI.

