- the study design (e.g., the number of participants);
- the details of each pain management regimen (including their risks and benefits);
- how patients are assigned to the investigational and control groups (i.e., randomly);
- the methods by which the study will monitor the patient's pain;
- risks/benefits;
- participation in this study is not required for receipt of either postoperative analgesia; regimen;
- patients may withdraw from this study at their discretion;
-

9. **EXPERIMENTAL DESIGN**

a. Overview:

This is a randomized, double-blind, placebo-controlled trial of serratus plane block in subjects undergoing unilateral or bilateral breast surgery at Long Island Jewish Medical Center. Ninety subjects will be enrolled into the study at presurgical testing approximately one week before their surgery. Subjects will be stratified based on surgery type and randomized to receive a serratus plane block with either bupivacaine HCL or normal saline in a 1:1 ratio. All patients will receive standard intraoperative anesthesia and standard postoperative pain control.

- **Control Group:** Each patient in the control group will receive standard intra-operative general anesthesia and standard post-operative pain control as well as a placebo injection of normal saline on the operated side(s) using the same technique as the serratus plane block.
- **Investigational Group:** Each patient in the investigational group will receive serratus plane blocks on the operated side(s) using bupivacaine HCl. This will be in addition to standard of care intra-operative anesthesia and standard of care post-operative pain control. One (unilateral) or two (bilateral) 20mL bolus of drug, 0.25% of bupivacaine.HCl, will be administered underneath the fascia of the serratus muscle for each subject using ultrasound guidance. The total amount of bupivacaine administered will be 50mg or 100mg for unilateral and bilateral procedures, respectively.

b. Randomization:

The Biostatistics Unit (BU) will develop a computer-generated randomization list that utilizes a permuted block design, and will develop and implement a well-documented double-blind randomization procedure. Details of the procedure, including required record keeping, will be further developed upon approval of this protocol.

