A unique randomization number will be generated by the Biostatistics Unit for each subject in the trial with the format RZxyyy. The randomization number will be a 4-digit number with the following format: the 1st digit (x) will designate the **TYPE OF SURGERY** [1=Breast reduction/mastopexy, 2=Breast augmentation, 3= Revisions & Other] and the last 3 digits (yyy) will be numbered sequentially starting with “001”. For example, the third subject randomized to “Breast augmentation” will have the randomization number RZ2003.

Subjects will be randomized to either Placebo (saline) or Bupivacaine injection as described below. Randomization will be double blind. Preparation of blinded injection is described below.

c. Blinding and Injection Preparation:

Sterile, sealed, plastic syringes of clinically available supply of normal saline (0.9%) and bupivacaine.HCl (0.25%) will be prepared aseptically by the unblinded study pharmacist ([name]) at Long Island Jewish Medical Center Pharmacy upon receipt of study physician's orders. The study pharmacist will have access to the full randomization scheme and will prepare the sterile syringe with a 2-part tear off label. Both parts of the label will contain a randomly generated 4-digit number generated by the Biostatistics Unit. In addition to noting the number, one

of these labels will be attached to the drug accountability paperwork when the drug is dispensed. The second part of the label will remain affixed to the syringe and will be attached to data collection sheet by the study anesthesiologist administering the drug. Syringes will be prepared upon receipt of study physicians orders. Any test articles to be administered will be checked by the pharmacist and a second member of LIJ pharmacy.

d. Surgery:

All breast surgery will be performed under general anesthesia as per standard of care. The type of surgery and laterality will be recorded.

1. Opioids will be utilized at the discretion of the study anesthesiologist for intraoperative pain control.
2. Regardless of whether a subject is enrolled in the investigational arm or control arm of the study, the breast surgery will take place in the usual fashion.

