4. **Statistical Methods:**

Primary - Analysis of covariance (ANCOVA) with “type of surgery” as a covariate will be used to compare mean ME between the two groups. (The inclusion of these covariates in the model is in accordance with ICH E9 Section 5.7 guidelines.) Data transformation (presumably a log transform) will be considered in order to achieve the required assumptions of normality and equal variance.

Secondary – The chi-square test will be used to compare anti-emetic rates and patient satisfaction. ANCOVA will be used to compare LOS, pain and nausea scores.

5. **Intention to Treat (ITT):** The ITT population will be defined as all subjects who are randomized. All primary analyses will be carried out on the ITT population.
6. **Sample Size Considerations:** A two-sample t-test approach is used as a reasonable simplification of the ANCOVA method. Based on previous data, it is expected that the Placebo group will average 12 ME (SD=4) of narcotics in the PACU. A reduction of 20% to 9.6 ME in the Bipuvacaine group would be clinically significant. A sample size of n=45 subjects per group (total 90) will yield 80% power to detect such a reduction (alpha=0.05, 2-tailed t-test).
7. **Interim Analysis:** There will be no interim analysis for early stopping of the trial.

j. Adverse events

An adverse event (AE) is any untoward medical occurrence in a clinical investigation of a patient administered a pharmaceutical product and that does not necessarily have a causal relationship with the treatment. An AE therefore is any unfavorable and unintended sign (including an abnormal laboratory finding), symptom or disease temporally associated with the administration of an investigational product, whether or not related to the investigational product. An unexpected AE is one of a type not identified in nature,

severity, or frequency in the study protocol or of greater severity or frequency than expected based on the information in the study protocol.

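### Laterality is recorded and plausibly predicts 4-hour opioid use, but the primary ANCOVA adjusts only for type of surgery; prespecifying it as a second covariate would be a nearly free gain in precision

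*Combined protocol and SAP*

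**What the plan says.** Section 9.a admits unilateral and bilateral operations and describes the allocation: "Subjects will be stratified based on surgery type and randomized to receive a serratus plane block with either bupivacaine HCL or normal saline". Section 9.b gives the strata three levels: reduction or mastopexy, augmentation, and revisions and other. None is defined by laterality.

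Laterality determines how many injections a patient receives and, in the active arm, the total drug: "The total amount of bupivacaine administered will be 50mg or 100mg for unilateral and bilateral procedures, respectively". Each operated side receives one 20 mL bolus of 0.25% bupivacaine, so the amount per side is constant.

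Section 9.d treats laterality as a variable distinct from surgery type: "The type of surgery and laterality will be recorded".

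In section 9.i.4 the primary analysis is an ANCOVA whose one adjustment factor is the surgical category, entered "as a covariate will be used to compare mean ME between the two groups". The sentence that follows speaks of covariates in the plural, but no second one is named. A transformation, probably logarithmic, is left open. No laterality covariate, subgroup or sensitivity analysis appears anywhere.

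Section 9.i.6 sizes the trial with a simple two-group t-test at the two-sided 5% level, for a fall from 12 to 9.6 ME with an SD of 4, and concludes: "A sample size of n=45 subjects per group (total 90) will yield 80% power to detect such a reduction". No gain from covariates is credited there.

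**The concern.** A patient with two operated breasts may well need more opioid in the first four hours than a patient with one. The plan already accepts the principle of adjusting for a baseline surgical factor, since it does so for type of surgery. Yet it leaves out a second such factor that it records anyway.

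If laterality predicts opioid use within surgery type, two things follow. Variation due to laterality stays in the error term and widens the confidence interval for the treatment difference. In addition, the arms of a 90-patient trial can differ by chance in their bilateral share, which moves the estimate in that particular trial. With planned power barely above 80%, there is little precision to spare. If a gap appeared and the adjustment were added only then, it would be open to challenge as post hoc.

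**Working it through.** **Inputs from the plan (section 9.i.6).** 45 per arm, difference 12 − 9.6 = 2.4 ME, SD 4, two-sided alpha 0.05.

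**The plan's own figure.** The standard error of the difference is 4 × √(2/45) = 0.843 ME. The noncentral t distribution gives 80.4% power at 45 per arm, and 44.6 per arm for exactly 80%, which rounds up to 45. The stated sample size reproduces.

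**Inputs that the documents do not give (assumed).**
- The bilateral share p, and how it varies by surgery type.
- The bilateral minus unilateral difference g within surgery type, taken as 0 to 4 ME. The upper end equals one full SD and exceeds the 2.4 ME treatment effect.
- SD 4 is taken as the SD before adjusting for laterality, and the analysis as being on the raw ME scale.

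**Precision.** Let v be the variance of the laterality indicator within surgery type. The share of variance explained is v·g²/16, and the residual SD is √(16 − v·g²).

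- *Scenario A: only one of three equal strata is mixed, and half of it is bilateral.* v = (1/3) × 0.25 = 0.083.
- *Scenario B: laterality unrelated to surgery type, half of all cases bilateral.* v = 0.25. This maximises v.

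| g (ME) | A: variance explained | A: power | B: variance explained | B: power |
|---|---|---|---|---|
| 0 | 0% | 80.4% | 0% | 80.4% |
| 1 | 0.5% | 80.6% | 1.6% | 81.0% |
| 2 | 2.1% | 81.2% | 6.3% | 82.8% |
| 4 | 8.3% | 83.7% | 25% | 90.2% |

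At g = 4 the residual SD is √(16 − 1.33) = 3.83 in A and √(16 − 4) = 3.46 in B. The standard error therefore falls by about 4% and 13% respectively.

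Simulation of intermediate cases (three strata of 30, assumed blocks of 4, assumed bilateral shares of 0.95/0.90/0.50 or 0.98/0.95/0.40) gave gains of about half a percentage point at g = 2 and 4 to 5 points at g = 4.

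**Chance imbalance.** With 45 per arm, a gap of 10 percentage points means a difference of at least 5 bilateral patients.
- Scenario A: only the 30 patients in the mixed stratum contribute, 15 per arm. The difference of two binomial(15, 0.5) counts is 5 or more in absolute value with probability 0.10.
- Scenario B: two binomial(45, 0.5) counts give 0.34. At a bilateral share of 0.3 or 0.7 the figure is 0.30. If exactly 45 of the 90 patients are bilateral and allocation ignores type, the figure is 0.40, because the difference then moves in odd steps.
- The intermediate simulated cases gave about 0.13 to 0.20.

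A 10-point gap shifts the unadjusted difference by 0.1 × g: 0.2 ME at g = 2 (0.2/2.4 = 8% of the target) and 0.4 ME at g = 4 (17%).

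**Validity.** In the same simulations, with laterality left out of the model, type I error was 4.6% to 5.6%, consistent with the nominal 5%.

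**Sensitivity to the meaning of SD 4.** If 4 is instead the SD within laterality, leaving laterality out lowers power. In scenario B, the total SD is √(16 + 0.25 × g²), giving 78.0% at g = 2 and 71.1% at g = 4. In scenario A, the corresponding powers are 79.6% and 77.2%. The documents do not say which reading applies.

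**The case against.** The strongest reply is that nothing in the plan is wrong. The stratification factor is also the model covariate, so design and analysis agree. Omitting one more prognostic variable leaves the comparison unbiased, and the sample size claims no covariate gain. All of this stands, and it makes the point an improvement rather than a correction.

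The second reply concerns size. The documents support no particular laterality effect, and surgery type may already capture much of laterality. This also stands. A reader who starts at 2 ME and treats laterality as unrelated to surgery type would infer a power gain to 82–90%. That is the favourable end of the range, not a neutral estimate.

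Third, a reader might infer from the 50 and 100 mg totals that dose confounds the comparison. The documents do not support this. The amount per operated side is constant and the totals differ only within the active arm. Laterality might modify the treatment effect, but a main-effect covariate would not address that.

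Fourth, a reader might conclude that laterality should become a stratification factor. Six strata for 90 patients may leave sparse cells and unfilled blocks, and the stratum is built into the randomisation number. That trade-off is debatable, and covariate adjustment does not need it.

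Finally, sections 9.c and 9.d do not say that the physician's order carries laterality. That it is known before randomisation is a reasonable inference from the number of boluses required, not a stated fact.

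**Conclusion.** The point holds as a free improvement of minor to moderate weight. The documents establish that both lateralities are eligible, that laterality is recorded apart from surgery type, and that the primary model does not use it. They do not establish how strongly it predicts opioid use, or how far surgery type already determines it.

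The benefit therefore runs from nothing at all, through about 3 percentage points of power (one mixed stratum, 4 ME), to an upper limit of about 10 points (laterality unrelated to type, half bilateral, 4 ME). The chance of a gap of 10 points or more is about 10% to 34% across the same scenarios. These figures assume a raw-scale analysis and would not carry over directly to log-transformed data.

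The stronger readings, that the primary result would be biased, its type I error inflated or the sample size miscalculated, are not supported. Randomisation protects the comparison and the 45 per arm reproduces.

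**What to change.** In section 9.i.4 (and the matching line of the study summary), name planned laterality, unilateral or bilateral, as a second covariate beside type of surgery in the primary ANCOVA, on whichever scale is finally analysed. Define it as the laterality planned before randomisation, so that it is a true baseline variable, and make sure that it is documented at that time. Tabulate it by arm with the baseline characteristics. Settle this before unblinding.

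Leave the randomisation strata and the sample size unchanged.

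The cost is one degree of freedom out of roughly 86 (90 patients less intercept, treatment and two surgery-type terms). Laterality is already being collected, so no new data item and no additional patients are needed.
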